### **Procedures performed for research purposes only:**

## **Statistical Methods, Data Analysis and Interpretation**

---

A two-way (group x time) repeated measures analysis of variance (ANOVA) will be used to compare change between groups in body composition, performance, and recovery. If a significance in group x time interactions occur, an independent t-test will be performed for each dependent variable between groups. An alpha level will be set at  $p < 0.05$ .

Sample size and power analysis: For a total of 60 participants, we anticipate a 30% attrition, leaving us with  $n=40$  ( $n=20$  per group). This provides  $>90\%$  power for detecting differences in our main outcome variables. Based on preliminary data, a similar study used  $n=18$  for their sample sizes. This sample size will be used for sample size calculations for a future well-

powered trial. Estimates for effect sizes will be implemented due to the limited sample size. Effect sizes ( $n^2$ ) will be defined as small (0.20), medium (0.50), and large (0.80).

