## Study Population

---

**Age of Participants:** 13-18 years old

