**Inclusion Criteria**

1. 13-18 years old; males and females
2. High school soccer players from Marsh Valley High School in Idaho
  - a. In season, competition and practices at least 6-days/week

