### **Procedures:**

**Informed Consent, Parental Permission and Assent:** These will be obtained over Zoom, prior to participation in any study procedures.

**Randomization:** Randomization will occur following pre-intervention testing. Participants will be randomized via random number generator stratified by sex, and blinded into either whey protein supplement group or placebo (isocaloric) control group.

**Pre- and Post-Intervention Testing Background:** Pre- and post-intervention testing will occur over a single day for each participant at the University of Utah campus. There will be three (3) separate days of pre-intervention and post-intervention testing. One day will be for members of the “Girls’ Soccer Team”. One day for members of the “Boys Soccer Team”. The final day will be a make-up day for participants who were unable to attend with their team, but wish to participate. According to the coaches, no student-athletes openly identify as non-binary nor transgender. However, in March of 2020 Idaho’s “Fairness in Women’s Sports Act” was signed in to law. While it has yet to go in to effect, if taken up, it will prohibit transgender women and girls from competing on teams that align with their gender identity in Idaho. Thus, it is possible that individuals may not be open about this. To address concerns re: outing anyone, participants will complete the testing day on their team’s assigned day, as mentioned above, or on the make-up day if they are not available on the main testing day. Furthermore, our strategy of having make-up testing options for both pre- and post-intervention means that not all members of each team will be tested on the same day. Thus, this mitigates potential risk of coercion as teammates will not know for sure who elected to participate or not in the trial.

**Selection of School:** Marsh Valley High School in Marsh Valley, ID was selected as the test site for this study due to the following connection:

The Track and Field coach at this school comes from a family of Dairy farmers and is also a Paralympic athlete who has had a relationship with the Western Dairy Center (study sponsor) for a number of years. He inquired with WDC about doing a trial on his student-athletes, so the WDC connected the PI ([name]) with this school for the trial. Due to large differences in athlete type and training load in track and field (sprinters, distance, jumpers, throwers),

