**Anthropometrics and Body Composition Assessment:** In a private room, all athletes will undergo non-invasive measurements of height and weight (which will be used to calculate BMI-percentile) (Kuczmarski, 2002). Each athlete will next be measured for body composition via the BodPod. The BodPod requires participants to wear spandex-like material or a sport-style bathing suit for the body composition assessment. Participants will be required to change into these clothing materials as well as wear a swim cap to cover the hair (as is required for this equipment). They will change in a private bathroom that is located in the same private room where the BodPod is located. Importantly, the scale in which participants will have their weight measured on does not have a display. The weight is displayed only on the computer, which participants will not see. Participants will not be provided with their BodPod results, and will not be aware of their weight, BMI percentile, nor body composition. As it is done in private, no other participants will see other's weight or body composition either. Participant body composition and anthropometric forms will be printed at a later time by study staff and added to participant folders and our REDcap Data Set when participants have left.

**Blood Sample:** A blood sample will be obtained via the antecubital vein, by a trained member of the CTSI Clinical Services Core (CSC). The sample will consist of about a tablespoon of blood. We will use blood samples to measure the following biomarkers: IL-6, follistatin,

adiponectin, FGF21, decorin, and cathepsin B (CTSB)(Chow et al., 2022). IL-6 will be measured to assess systemic inflammation. Follistatin is measured to assess long-term muscle growth. Adiponectin is measured to assess inflammation. FGF21 is measured to assess the function of various metabolic pathways. Decorin is measured to assess inflammation. CTSB is measured to assess correlating protein levels in the blood. Blood samples will be centrifuged, and plasma samples will be stored in a -80-degree freezer for batch analysis at the end of the study. Study provided bagels will be distributed after the blood draw.

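### Entry spans ages 13 to 18, but age is in neither the randomisation nor the model, so age-related change stays in the error term and a chance age gap between arms goes uncorrected

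*Combined protocol and SAP*

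**What the plan says.** All references are to the combined protocol and SAP.

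- **Who enters.** Inclusion Criteria: "13-18 years old; males and females", all soccer players at one high school.
- **How they are allocated.** Procedures, under Randomization: "Participants will be randomized via random number generator stratified by sex". Neither age nor any maturity measure is used.
- **How they are compared.** Statistical Methods, Data Analysis and Interpretation: the factors are arm and visit, and a "repeated measures analysis of variance (ANOVA) will be used to compare change between groups in body composition, performance, and recovery". A significant interaction leads to a second step, in which "an independent t-test will be performed for each dependent variable between groups". No covariate appears, so the stratification factor, sex, is also missing from the model.
- **Where age is used.** Under Anthropometrics and Body Composition Assessment, height and weight are taken, "which will be used to calculate BMI-percentile". That is the only age-referenced measure. The BodPod, 1.5-mile run, sprint, strength and endurance outcomes have none.

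**The concern.** Athletes across this age range may change at different rates in mass, lean tissue, strength and speed over 10 or 12 weeks, with or without a supplement. The group-by-time contrast removes stable differences in level between younger and older athletes. It does not remove differences in rate of change, and change is what the trial compares.

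Two things follow. Any age-related change widens the error of the whey comparison. And if one arm happens to be older, the estimate moves by an amount that the trial's own data could estimate and remove, but the plan does not do so.

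The follow-up t-test adds an ambiguity, because the plan does not say whether it uses change or post-intervention values. If it uses post-intervention values, age differences in level come back as well.

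The results are also meant to feed sample-size calculations for a later trial, so an error SD inflated by age, or an estimate shifted by it, would carry forward.

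**Working it through.** **The plan's own figure.** The plan states more than 90% power with 40 completers, 20 per group, from 60 enrolled. (60 × 0.70 = 42, close to the stated 40.) It gives no target effect, SD or named main outcome, so the power cannot be reproduced. A two-sided 0.05 t-test with 20 per arm reaches 90% only at a standardised difference of about 1.05. The stated power therefore neither supports nor weakens this point.

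**Inputs.** From the documents: 20 per arm and alpha 0.05 (sidedness not stated; two-sided assumed). Assumed, because the documents give neither:
- the SD of age, 1.0 to 1.73 years. The top value is ages spread evenly over six full years, 6/√12 = 1.73;
- r, the within-arm correlation of age with the outcome compared, 0 to 0.5.

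The effect is set at d = 0.8, the plan's label for large, read here as a difference in SD units.

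**1. Chance age gap.** SE of the gap = SD × √(2/20).

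| Age SD (y) | SE of gap (y) | 0.5/SE | P(gap ≥ 0.5 y) |
|---|---|---|---|
| 1.0 | 0.316 | 1.58 | 11% |
| 1.2 | 0.379 | 1.32 | 19% |
| 1.5 | 0.474 | 1.05 | 29% |
| 1.73 | 0.547 | 0.91 | 36% |

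**2. Shift from an uncorrected gap.** Shift in outcome SDs = r × gap / SD of age. For a 0.5-year gap and SD 1.5: 0.2 × 0.5/1.5 = 0.07; 0.3 gives 0.10; 0.5 gives 0.17.

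**3. Power with age in the model.** Adjustment multiplies the variance of the treatment estimate by (1 − r²). Estimating the age slope costs, on average, a further factor of 1 + 1/36 = 37/36 with 40 athletes. Unadjusted: noncentrality 0.8 × √10 = 2.530 on 38 df, power 69.3%. Adjusted: noncentrality 2.530/√[(1 − r²) × 37/36] on 37 df.

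| r | Variance factor | Efficiency gain | Noncentrality | Power |
|---|---|---|---|---|
| 0 | 1.028 | −2.7% | 2.495 | 68% |
| 0.1 | 1.018 | −1.7% | 2.508 | 69% |
| 0.2 | 0.987 | 1.4% | 2.547 | 70% |
| 0.3 | 0.935 | 7% | 2.616 | 72% |
| 0.5 | 0.771 | 30% | 2.881 | 80% |

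These figures isolate the age term. Adding the baseline value and sex would have its own effect, not counted here.

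**4. Type I error.** Simulation of 40,000 null trials with ages uniform over 13 to 18; the age-adjusted model was fitted to 10,000 of them.

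| | r = 0.3 | r = 0.5 |
|---|---|---|
| Unadjusted, all allocations | 5.0% | 5.0% |
| Unadjusted, age gap beyond 1 SE | 6.6% | 8.8% |
| Unadjusted, age gap beyond 1.96 SE | 9.4% | 17.2% |
| Age-adjusted, age gap beyond 1 SE | 4.7% | 5.1% |

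**The case against.** The strongest reply is that the trial is randomised. Chance age gaps are already covered by the 5% error rate, and the planned test is valid without adjustment. That stands. A reader might infer that omitting age gives the trial an excess of false positives, so that an age gap passes for a whey effect. The documents do not support this: averaged over allocations the error is 5%, and in an unlucky allocation a gap can hide an effect as easily as imitate one. The limit is that the analysis rests on 40 completers of 60, so the argument assumes that dropout does not depend on age and arm together.

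A reader might also infer that the bias has a known direction. The documents do not say how age relates to change in any outcome, and the sign may differ between lean mass, sprint time and strength. The direction can only be estimated from the data.

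It is also fair to say that the benefit rests on an assumed correlation, that 13 to 18 is an eligibility limit and not an observed spread, and that growth stage is not the same as age. All three stand. They are why the ranges above run down to r = 0 and an age SD of 1.0, and why age is offered only as a partial proxy for maturation.

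Finally, the trial presents itself as preliminary. That lowers the stakes, but the fix needs no new data.

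**Conclusion.** The concern holds as a matter of precision and of bias conditional on the allocation obtained; it is not an error that invalidates the planned test. It is certain from the documents that age enters neither the allocation nor the model. How much this matters is not, because it depends on two quantities that the documents do not give. With an age SD of 1.0 to 1.73 years, an arm gap of half a year or more has an 11% to 36% chance. With d = 0.8 and 20 per arm, adjustment is worth about 3 power points at r = 0.3 and 11 at r = 0.5. It is worth almost nothing at 0.2, and it costs slightly at 0.1 and below. This is a cheap improvement with a small, known downside.

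**What to change.** In Statistical Methods, Data Analysis and Interpretation, pre-specify baseline age (continuous) as a covariate in the between-arm comparison of each performance and body-composition outcome. Include the outcome's baseline value and sex in the same model; the current plan has neither. Exempt BMI-percentile, which is already age-referenced. An ANCOVA on the post-intervention value would do this, and would also settle which values the follow-up t-test was meant to compare. With about 40 athletes, covariate adjustment is more practical than adding age strata to the randomisation.

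The cost is one sentence in the plan, one degree of freedom for age, and about one power point (69% to 68%) if age turns out to be unrelated to change. Age must already be known for eligibility and BMI-percentile, so no visit or measurement is added. The choice should be fixed before the data are seen, because adding age only after finding an imbalance would be data-driven. The report should say that chronological age captures maturation only in part.

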
## Purpose and Objectives

---

The overall aim of the proposed project is to compare protein supplementation on performance, recovery, and body composition changes in adolescent soccer players between the whey protein and the control group in response to the 10-week intervention. Hypothesis: We hypothesize that the whey protein group will demonstrate more favorable changes in

performance, recovery, and body composition outcomes than the control group following the 10-week supplementation period.

Secondary outcomes will include investigating interactions between sleep physiology and dietary protein on muscle recovery and performance following the 10-week intervention.

*Hypothesis:* Sleep efficiency will be higher in the whey protein supplementation group versus the placebo control. *Exploratory* analyses will examine the impact of whey protein supplementation on dimensions of sleep including duration, regularity, satisfaction, alertness, timing, and sleep staging (e.g., stage N1, N2, SWS, rapid eye movement (REM))

The **expected outcomes** will provide support for whey protein supplementation to enhance exercise performance, recovery, and body composition in adolescent, team-sport athletes. Completion of the proposed objectives (see below) will add to the sparse evidence base on protein supplementation in this unique, athletic population, and provide preliminary data for future investigations in this area. Specifically, future work could address both mechanistic questions as well as evaluation of other protein options, such as milk consumption, which could be a more cost-effective and acceptable option for youth athletes.

Objective 1: Compare the impact of 10-weeks of whey protein vs. isocaloric control on performance in high school soccer players.

Objective 2: Compare the impact of 10-weeks of whey protein vs. isocaloric control on body composition in high school soccer players.

Objective 3: Compare the impact of 10-weeks of whey protein vs isocaloric control on hunger and satiety in high school soccer players

Objective 4: Compare the impact of 10-weeks of whey protein vs. isocaloric control on sleep duration and quality in high school soccer players.

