**Inclusion Criteria:**

A total of 60 subjects are expected to enroll in this trial with a total of 40 completing the study protocol in its entirety to perform statistical analyses on our primary outcomes. We will recruit soccer players between the ages of 13-18 who are healthy, have no underlying metabolic diseases and have no contraindications to exercise.

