**Cardiorespiratory Fitness Testing:** Athletes will then be escorted by study personnel to the university track and field to begin field testing. Athletes will perform a *1.5-mile test*, and a *30-yard sprint* test to measure fitness. The purpose of the 1.5-mile test is to evaluate how fast athletes can run, covering an allotted distance. This test will measure how much oxygen is being used by the muscle in a field test. The purpose of the sprint test is to assess athletes rapidly accelerating from a standing position and to measure their maximal speed over a short distance.

**Muscular Fitness Testing:** Finally, athletes will perform muscle strength and endurance tests. Muscle endurance will be measured by having our participants contract their leg muscles against a specific force at a particular speed for a certain number of repetitions. Muscle strength will be assessed by having the participants contract their leg muscles with as much force as possible against a non-movable bar.

**Sleep measures:** After baseline testing ends, and before participants leave, each participant will be provided with a Fitbit® watch (Inspire 2). Fitbit's will be used measure sleep efficiency, duration, regularity, timing, and staging, similar to prior studies. We will use a program called Fitabase to collect the data from each Fitbit®. Participants will be instructed to wear their Fitbit® for 1-week straight (except during training times and when they are showering/getting wet) so that baseline sleep habits can be evaluated. Participants will be able to keep their Fitbit® after the study ends.

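### No primary outcome variable is named and every variable in three domains is tested at an unadjusted 0.05, so with an assumed 6 to 13 outcomes the chance of some false-positive group difference is well above 5%

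*Combined protocol and SAP*

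**What the plan says.** Under Statistical Methods, Data Analysis and Interpretation, a two-way repeated-measures ANOVA "will be used to compare change between groups in body composition, performance, and recovery". After a significant interaction, "an independent t-test will be performed for each dependent variable between groups". The threshold is common to all of them: "An alpha level will be set at" p < 0.05. The section gives no adjustment for multiple outcomes, no order of testing and no composite. It claims more than 90% power for the main outcome variables without saying which they are.

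The Inclusion Criteria text expects 40 completers "to perform statistical analyses on our primary outcomes", in the plural and again unnamed.

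Purpose and Objectives puts performance, recovery and body composition together in one directional hypothesis ("We hypothesize that the whey protein group will demonstrate more favorable changes in" all three) and places sleep below them: "Secondary outcomes will include investigating interactions between sleep physiology and dietary protein on muscle recovery and performance". The four numbered objectives cover performance, body composition, hunger and satiety, and sleep. None of them concerns recovery.

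The Procedures and Intervention sections supply the candidate variables: a 1.5-mile run and a 30-yard sprint; leg tests ("Finally, athletes will perform muscle strength and endurance tests"); BodPod composition and BMI percentile; a muscle-soreness (DOMS) questionnaire; and six blood markers ("We will use blood samples to measure the following biomarkers: IL-6, follistatin" and four more).

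**The concern.** When several variables are each tested at 0.05 and none is designated in advance, the 5% error rate applies to each test and not to the conclusion of the trial. Which variable carries that conclusion can then be settled after the results are known. Because recovery is undefined, so can the question of whether the blood markers belong to the main hypothesis.

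The two-step sequence does not help across outcomes. The interaction test that opens the t-test is itself run at 0.05, separately for each variable.

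At stake is how far a significant finding can be taken as support for the hypothesis. The power claim is affected too: without a named variable there is no effect or standard deviation to check it against.

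**Working it through.** **The plan's own figure.** The only related number is power above 90% with 20 per group. It cannot be reproduced, because no target difference or SD is given, only generic effect-size labels of 0.20, 0.50 and 0.80. For a two-group t-test with n = 20 per group and two-sided 0.05 (noncentral t):

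- standardised difference 0.5: power 34%
- standardised difference 0.8: power 69%
- 90% power needs a standardised difference of about 1.05

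On change scores, SD of change = SD × √(2(1 − r)), where r is the pre-post correlation. A difference of 0.8 baseline SD then has power 69%, 89% or 97% at r = 0.5, 0.7 or 0.8 (assumed values). The claim may therefore be true for some variable under some assumptions, but the documents do not say which.

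**Counting outcomes (an assumption).** The documents list measurements, not dependent variables.

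- 6: 1.5-mile run, sprint, leg strength, leg endurance, one BodPod variable, DOMS.
- 10: those six plus the four markers that Procedures links to inflammation or muscle growth (IL-6, follistatin, adiponectin, decorin).
- 12: all six markers added to the first six.
- 13: one more body-composition variable, such as BMI percentile or a second BodPod variable.

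**Family-wise error, independent tests, no true effect on any outcome.** A positive is a significant interaction at 0.05.

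- Either direction: 1 − 0.95^k
- Favouring whey only: 1 − 0.975^k

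| k | Either direction | Favouring whey |
|---|---|---|
| 1 | 5.0% | 2.5% |
| 6 | 1 − 0.735 = 26.5% | 1 − 0.859 = 14.1% |
| 10 | 1 − 0.599 = 40.1% | 1 − 0.776 = 22.4% |
| 12 | 1 − 0.540 = 46.0% | 1 − 0.738 = 26.2% |
| 13 | 1 − 0.513 = 48.7% | 1 − 0.720 = 28.0% |

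**Correlated tests.** Simulation of k equally correlated normal test statistics, 200,000 replicates, cut-off 1.96, each oriented so that positive favours whey. Cells give either direction / favouring whey.

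| Correlation | k = 6 | k = 12 | k = 13 |
|---|---|---|---|
| 0.3 | 24.2% / 12.2% | 39.7% / 20.2% | 41.9% / 21.5% |
| 0.5 | 20.9% / 10.4% | 32.0% / 16.0% | 33.4% / 16.8% |
| 0.7 | 16.2% / 8.1% | 23.3% / 11.6% | 24.1% / 12.1% |

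The documents give no correlations, so these are a sensitivity range. At 0.5 with six outcomes, the whey-favouring rate is 10.4 / 2.5 ≈ 4 times that of a single two-sided test.

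**Effect of a remedy.** One named primary variable at 0.05 returns the primary claim to 5%. Bonferroni over everything would use 0.05/6 = 0.0083 or 0.05/13 = 0.0038 and give a family-wise rate of about 4.9%. At an assumed standardised difference of 0.8, however, power would fall from 69% to 41% (6 outcomes) or 31% (13 outcomes).

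**The case against.** Four points can be made for the plan.

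*The study is partly preliminary.* Purpose and Objectives speaks of preliminary data, and Statistical Methods says the sample will inform a later, well-powered trial and that effect sizes will be estimated because numbers are limited. In such a study, strict family-wise control is partly a matter of preference. This stands as mitigation. It does not settle the matter, because the same document claims more than 90% power and expects outcomes that support whey supplementation.

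*There is already a hierarchy.* Sleep sits below the three main domains. That is correct, but no variable is singled out within those domains, and it is there that the 6 to 13 tests arise.

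*The outcomes are correlated.* Tests of fitness and strength in the same athletes probably are, and this lowers the rates. At correlation 0.7 with six outcomes the either-direction rate is 16%, still about three times nominal.

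*No rule says that one positive result is enough.* This is also correct. A reader might infer that a single significant variable establishes the hypothesis, but the hypothesis joins the three domains with an and, and no success rule is written. If every variable had to be significant, the false-positive rate could not exceed 5%. The defect is that the rule is missing.

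A reader might also take the 26–49% range as the chance of a false finding in favour of whey. It is not: it counts differences in either direction and assumes independence.

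**Conclusion.** The point holds in a limited form. No primary variable is named, every variable in three loosely bounded domains is tested at an unadjusted 0.05, and nothing says what would count as success.

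For 6 to 13 outcomes, the chance of at least one false-positive group difference in either direction is about 26–49% under independence and 21–33% at correlation 0.5. For whey-favouring differences it is 14–28% and 10–17%. These figures rest on three assumptions: the outcome count, the correlation, and no true effect on any outcome. They describe the risk of some false-positive test, not of a false claim under a rule in the plan. This should be corrected before unblinding; it does not invalidate the design.

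**What to change.** Before unblinding:

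1. Name one primary outcome variable, with its time point and analysis, and test only that at two-sided 0.05.
2. List the variables in each domain, including which, if any, of the blood markers count as recovery.
3. Make the remaining outcomes secondary with Holm adjustment within domain, or label them exploratory, reported as estimates with 95% confidence intervals and no efficacy claim. The exploratory option fits the stated role of informing a later trial.
4. Tie the power statement to the named variable, with its assumed difference and SD (and pre-post correlation if change is analysed), or withdraw it.

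No new data or participants are needed, but the change has costs. Fewer secondary results can be called significant, and adjusted secondary tests lose power. Restating the power needs inputs that the documents do not contain. The sponsor must also choose the primary variable: 1.5-mile run time under Objective 1 is one candidate, but nothing in the documents ranks it above the other measures.

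### The interaction test followed by an unadjusted t-test leaves sex out of the model and the second step undefined; one ANCOVA on baseline and sex would be clearer and somewhat more powerful

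*Combined protocol and SAP*

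**What the plan says.** In the combined protocol and SAP, the section on Statistical Methods, Data Analysis and Interpretation gives the whole inferential plan in a few lines. A two-way (group by time) repeated-measures ANOVA "will be used to compare change between groups in body composition, performance, and recovery". If the interaction is significant, "an independent t-test will be performed for each dependent variable between groups". One significance level, 0.05, applies throughout. No covariate is named.

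The Randomization paragraph under Procedures says: "Participants will be randomized via random number generator stratified by sex". Both sexes are eligible ("13-18 years old; males and females"). The next paragraph, on testing background, adds: "There will be three (3) separate days of pre-intervention and post-intervention testing". One is for the girls' team, one for the boys' team and one is a make-up day, so sex largely sets the testing day, though not completely.

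The analysis section does not say:
- whether the t-test uses post values or change scores;
- which time point it uses for outcomes measured repeatedly;
- whether it must be significant before an effect is claimed.

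**The concern.** Sex was thought important enough to stratify on, and it is largely tied to the testing day, yet it enters no model. Run time, sprint time, strength and body composition can be expected to differ between boys and girls of this age. Each athlete's own baseline predicts the post value, but it is used only through subtraction, which is less efficient than using it as a covariate.

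The second step adds a separate problem. Two analysts following the text could run different t-tests on the same data and reach different conclusions. With about 40 completers, and results meant to inform the sample size of a later trial, the study needs one precise between-group estimate per outcome. The t-test is planned only after a significant interaction, so the other outcomes have no planned between-group follow-up.

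**Working it through.** **The plan's own figure.** The plan expects 60 enrolled and 40 completing, 20 per group, with power above 90%. It gives 30% attrition, and 60 × 0.70 = 42; 40 of 60 is a 33.3% loss. This is close enough not to matter here. The power figure cannot be reproduced, because no effect size, SD or pre-post correlation is stated. A two-sided t-test with 20 per arm has 69% power at a standardised difference of 0.8, and needs about 1.05 for 90%.

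**Inputs.** From the documents: 20 per arm, alpha 0.05, randomization stratified by sex, and pre and post values from the same tests. Assumed: two-sided tests, within-sex SD of 1, within-sex pre-post correlation r, a sex gap g constant over time, equal numbers of boys and girls in each arm, and a true effect d in within-sex SDs.

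**Error SD and standard error of each test.** The SE is the SD × √(2/20) = SD × 0.316.
- Interaction (with two time points, F = t² of the change-score t-test): SD = √(2(1 − r)). Baseline is used through the change, and a constant sex gap cancels.
- t-test on change: the same test as the interaction.
- t-test on post values: SD ≈ √(1 + g²/4). Baseline is dropped and the sex gap sits in the error.
- ANCOVA on baseline and sex: SD = √(1 − r²), with 40 − 4 = 36 error degrees of freedom against 38.

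**Example with r = 0.8, g = 1.5.** The effect giving 90% power for the interaction is 1.0517 × √(2 × 0.2) = 0.665.
- Interaction: SE = 0.632 × 0.316 = 0.200; 0.665/0.200 = 3.3.
- Post values: SE = √(1 + 2.25/4) × 0.316 = 1.25 × 0.316 = 0.395; 0.665/0.395 = 1.7.
- ANCOVA: SE = √(1 − 0.64) × 0.316 = 0.6 × 0.316 = 0.190; 0.665/0.190 = 3.5.

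The average 95% interval width in simulation is 1.61 SD for post values and 0.77 SD for ANCOVA. For change it is about 2 × 2.02 × 0.200 = 0.81 SD. The wide interval therefore belongs to the post-value version alone.

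**Simulated power** (2,000 to 20,000 trials per figure; repeat runs differ by about 1 to 2 points):

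| r | sex gap (SD) | effect (SD) | interaction | post t-test | both steps | ANCOVA + sex |
|---|---|---|---|---|---|---|
| 0.8 | 1.5 | 0.67 | 90% | 34% | 32% | 92% |
| 0.8 | 0 | 0.67 | 90% | 54% | 50% | 92% |
| 0.5 | 1.5 | 1.05 | 89% | 77% | 72% | 95% |
| 0.5 | 0 | 1.05 | 90% | 90% | 83% | 96% |
| 0.5 | 0 | 0.80 | 69% | 69% | 54% | 80% |
| 0.7 | 1 | 0.80 | 89% | 60% | 56% | 93% |

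ANCOVA's gain over the interaction alone is about 2 points at r = 0.8, 5 to 6 at r = 0.5 with an effect of 1.05, and 11 at r = 0.5 with an effect of 0.8. At r = 0.9 it falls below 1 point when the interaction has 90% power, which is within simulation error.

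On the post-value version, the share of significant interactions followed by a non-significant t-test is 1 − 0.324/0.896 = 64% in the first row and 1 − 0.828/0.899 = 8% in the fourth. On change scores it is zero.

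**No true effect.** The interaction alone rejects in about 5% of trials. Requiring both steps, on post values, rejects in under 1% when r is 0.5 or more.

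**The case against.** A reader might infer that the plan ignores baseline and that true effects will often pass the interaction and then be lost at the t-test. The documents do not support this, for three reasons.

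- The interaction is a comparison of change. It uses every baseline value, and a sex difference that is constant over time drops out of it.
- The text does not say that the t-test must be significant. It can be read as a descriptive follow-up.
- The text does not say that the t-test uses post values. The sentence before it is about change, and on change scores with two time points the two steps cannot disagree.

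The size of any conflict also depends on a correlation and a sex gap that appear nowhere in the documents. Fixing the interaction's power at 90% makes the effect smaller in post-value SDs as r rises, so the post-value test is bound to look worse at high r. Finally, nothing here shows bias or excess false positives, and the protocol presents its results as preliminary data for later work.

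All of this stands, and it limits the point to efficiency and ambiguity. It does not supply what is missing: the t-test's variable, time point and role are undefined, and the stratification factor is in no model. On neither version does the second step help. It either adds nothing or discards information.

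**Conclusion.** The point holds as an efficiency and specification issue that should be fixed. Against the interaction test alone, ANCOVA with baseline and sex gains about 2 to 11 points of power in the tabulated scenarios with 20 per arm. The gain is larger at lower correlation and negligible near r = 0.9.

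The much larger contrast, about 32% to 83% for both steps against 92% to 96% for ANCOVA in the four tabulated scenarios with interaction power near 90%, requires two things the plan does not state: that the t-test is on post values, and that it must be significant. It should be cited only with those conditions. More extreme assumptions widen it; r = 0.9 with a 2 SD sex gap gives about 9% for both steps.

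All figures rest on assumed correlations, sex gaps, effects and an equal sex split. The harm is lost power and an unclear conclusion. A reader should not infer that the planned interaction test is invalid or that false positives are inflated.

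**What to change.** For outcomes measured before and after the intervention, replace both steps with one ANCOVA of the post value on group, baseline value and sex. Report the adjusted group difference with its 95% CI and p-value for every outcome, significant or not, and drop the conditional t-test.

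For outcomes collected every two weeks (sleep, PSQI, GI symptoms, DOMS), use a mixed model with group, time, group by time, sex and the baseline value where there is one, with a single prespecified contrast at the end of the intervention. The baseline questionnaires listed under Pre-Intervention Procedures do not include DOMS, so that model would have no baseline term unless one is collected.

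The cost is SAP wording and two model degrees of freedom (38 to 36). Sex is already needed for randomization, and baseline values are already collected for the pre/post outcomes.
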